#### 8.1.4 Cytokine arrays

If fresh frozen biopsy specimens are available, they may be used in a cytokine array analysis by a well-established protocol in the [name] Lab using a commercially available cytokine protein array (R&D).

### 8.2 Serum and Plasma Marker Studies

Various factors may impact the immunomodulatory properties and efficacy of nivolumab and ipilimumab will be investigated in peripheral blood specimens taken from all subjects prior to or during treatment. Data from these investigations will be evaluated for associations with response, survival, and/or safety (adverse event) data. Plasma samples will be obtained at time-points indicated in the **Study Calendar (Section 9)**. Non-invasive genomic approaches may be used in order to determine somatic mutations that detect residual disease in the patient's circulation.

Several analyses will be completed and are described briefly below.

#### 8.2.1 circulating tumor DNA (ctDNA)

Using blood samples collected prospectively after initiation of study treatment, measurements of cancer-specific genomic alterations in ctDNA may be analyzed to assess if they can predict disease progression prior to conventional CT imaging. Comparison of detection of somatic mutations in ctDNA and the sensitivity and specificity of the plasma analysis approach for detection of somatic alterations may be evaluated by comparison of the mutation data from the plasma to the sequence information obtained from analysis of the matching tumor samples.

Tumor- specific mutations found in the circulation after disease progression may be compared to the genomic profile of the recurrent tumors and the presence of matching resistance mutations in ctDNA may be confirmed.

#### 8.2.2 Peripheral Blood Mononuclear Cells (PBMCs)

PBMCs taken at time points on **Study Calendar (Section 9)** may be analyzed by flow cytometry or other methods (e.g., ELIspot) to assess immune cell activity.

#### 8.2.3 Serum Soluble Factors

To understand the prevalence of circulating proteins and the impact they may have on the clinical activity of nivolumab and ipilimumab, the protein concentrations of a panel of cytokines, chemokines, and other relevant immunomodulatory, serum-soluble factors (e.g., soluble PD-L1) may be investigated at baseline and during treatment.

#### 8.2.4 Single Nucleotide Polymorphisms (SNPs)

Whole blood will be collected from all subjects prior to treatment to generate genomic DNA for SNP analyses and serve as a reference for tumor mutational profiling. These analyses will focus on SNPs within genes associated with PD-1 and other immunoregulatory signaling pathways to determine if natural variation within those genes is associated with response to nivolumab and/or with AEs during treatment.

## 9. STUDY CALENDAR

	Screening (0-28 day pre-dose)	Cycle 1			Cycle 2, 3, etc.			End of Treatment (EOT) Assessment n	Follow-Up Visit 30 days post EOT/ 90 days post EOT	Survival/ FU visits l
		D1	D15	D29	D1	D15	D29			
CLINICAL ASSESSMENTS										
Informed consent	X									
Inclusion/Exclusion Criteria	X									
Demographics	X									
Medical history	X									
Physical exam o	X	X	X	X	X	X	X	X	X	
Vital signs, Height (baseline), Weight, O 2 Sat	X	X	X	X	X	X	X	X		
Height (baseline), Weight, O 2 Sat	X	X	X	X	X	X	X	X		
ECOG performance status	X	X	X	X	X	X	X	X	X	
CBC w/diff, plts	X	X f	X f	X f	X f	X f	X f	X	X	
Serum chemistry a	X	X f	X f	X f	X f	X f	X f	X	X	
Hepatitis Panel b	X									
TSH, Free T4, Free T3 c	X				X			X		
EKG	X	X f								
Urinalysis	X									
Pregnancy Test (WOCBP only) d	X	X			X					
Tumor Assessment/Imaging e	X				X				X m	
TREATMENT										
Nivolumab		X g	X g	X g	X g	X g	X g			
Ipilimumab		X g			X g					
CORRELATIVE STUDIES										
Archival Tumor h	X									
Fresh Tumor Biopsy i (Second stage only)	X				X					
Plasma for Immunogenecity Studies (Second stage only) j		X	X	X	X				X	
Plasma for ctDNA (Second stage only) j		X	X	X	X				X	
OTHER ASSESSMENTS										
Concurrent meds	X	X	X	X	X	X	X	X	X	
Symptom/Toxicity Assessment j	X	X	X	X	X	X	X	X	X	

Survival Status/Subsequent Therapy									X
	
a: LDH, AST, ALT, ALP, T. bili, BUN or serum urea level, creatinine, albumin, Ca, Mg, Na, K, Cl, phosphate, glucose, amylase, lipase, TSH, Free T4, Free T3, within 14 days prior to first dose.
 
b: Hep B/C (HBV sAg, HCV antibody or HCV RNA), within 28 days prior to first dose.
 
c: Thyroid Function Testing to be evaluated every 6 weeks
 
d: A serum or urine pregnancy testing is required prior to study enrollment/registration, also within 24 hours prior to D1 (and extension to 72 hours may be granted if unable to obtain within 24 hrs). Must be reassessed every 4 weeks.
 
e: CT scan of the chest and other relevant sites as well as MRI brain with gadolinium (or CT scan brain with contrast if MRI is contraindicated) will be performed <math>\leq</math> 4 weeks prior to the start of therapy. For subsequent scans, may be done within +/- 7 days of intended visit.
 
f: Within 72 hrs prior to dosing to include CBC w/ differential, AST, ALT, ALP, T. bili, BUN or serum urea level, creatinine, albumin, Ca, Mg, Na, K, Cl, LDH, phosphate, glucose, amylase, lipase, TSH (with reflexive Free T4 and Free T3). Note: C1D1 labs do not need to be repeated if they were performed within 14 days of dosing.
 
g: All treatments may be performed +/- 2 days of the intended treatment administration dates schedule for all cycles.
 
h: Recent sample or archival obtained. One (1) formalin-fixed paraffin embedded tumor tissue block or a minimum of 10 unstained tumor tissue sections are acceptable.
 
i: Mandatory fresh tissue will be collected for biomarker studies at baseline and on treatment (week 6-8) for patients enrolled in the second stage of the study.
 
j: Immunogenecity samples should be collected just before the administration of the first drug (preferably within 30 minutes).
 
k: Adverse event evaluation as per Common Terminology Criteria for Adverse Events (CTCAE) version 4.0
 
l: Survival follow-up may be done via phone call for survival status and subsequent therapy
 
m: CT if the subject came off study for reasons other than PD
 
n: EOT assessments do not need to be repeated if performed within 14 days
 
o: In order to minimize the need for research-only in-person visits, telemedicine visits may be substituted for in-person clinical trial visits or portions of clinical trial visits where determined to be appropriate and where determined by the investigator not to increase the participant's risks. Prior to initiating telemedicine for study visits the study team will explain to the participant, what a telemedicine visit entails and confirm that the study participant is in agreement and able to proceed with this method. Telemedicine acknowledgement will be obtained in accordance with the Guidance for Use of Telemedicine in Research. In the event telemedicine is not deemed feasible, the study visit will proceed as an in-person visit. Telemedicine visits will be conducted using HIPAA compliant method approved by the Health System and within licensing restrictions.
								

## 10. DATA REPORTING / REGULATORY REQUIREMENTS

### 10.1 Data Management

Interim analysis of toxicity, outcome and ongoing scientific investigations will be performed at least annually by the Sidney Kimmel Comprehensive Cancer Center Data Safety Monitoring Board (SKCCC DSMB). The SKCCC DSMB Recommendation letter will state the timeline for the next required review. The SKCCC DSMB will review aspects of this trial that are outlined in the responsibilities section of the Data and Safety Monitoring Board (DSMB) Guidance. If the committee decides that amendments should be made to this trial, recommendations will be made in writing to the Study Principal Investigator. The study team will submit modifications to the IRB within 60 days of receipt from the DSMB. The Associate Director of Clinical Research, will arbitrate any disagreements between the DSMB and the study Principal Investigator. These changes may include early termination of accrual if deemed appropriate.

The SKCCC Compliance Monitoring Program will provide external monitoring for JHU-

affiliated sites in accordance with SKCCC DSMP (Version 6.0, 02/21/2019). The SMC Subcommittee will determine the level of patient safety risk and level/frequency of monitoring.

## **10.2 Safety Meetings**

Scheduled meetings will take place at least on a monthly basis with the frequency dependent on the rate of subject accrual and will include the principal investigator, study coordinator(s), data manager(s), sub-investigators (as appropriate), collaborators (as appropriate), and biostatisticians (as appropriate) involved with the conduct of the protocol. During these meetings matters related to the following will be discussed: safety of protocol participants, validity and integrity of the data, enrollment rate relative to expectation, characteristics of participants, retention of participants, adherence to protocol (potential or real protocol violations), data completeness, and progress of data for objectives.

## **10.3 Monitoring**

The PI shall internally monitor the progress of the trial, including review and confirmation of all safety/treatment-related outcomes, response assessments, safety reports and/or any related source documentation.

# **11. MEASUREMENT OF EFFECT**

## **11.1 Antitumor Effect**

For the purposes of this study, patients should be re-evaluated every 6 weeks. In addition to a baseline scan, confirmatory scans will also be obtained 6 (not less than 4) weeks following initial documentation of an objective response.

Response and progression will be evaluated in this study using the new international criteria proposed by the revised Response Evaluation Criteria in Solid Tumors (RECIST) guideline (version 1.1). Changes in the largest diameter (unidimensional measurement) of the tumor lesions and the shortest diameter in the case of malignant lymph nodes are used in the RECIST criteria.

### **11.1.1 Definitions**

Evaluable for objective response. Only those patients who have measurable disease present at baseline, have received at least one cycle of therapy, and have had their disease re-evaluated will be considered evaluable for response. These patients will have their response classified according to the definitions stated below. (Note: Patients who exhibit objective disease progression prior to the end of cycle 1 will also be considered evaluable.)

Evaluable Non-Target Disease Response. Patients who have lesions present at baseline that are evaluable but do not meet the definitions of measurable disease, have received at least one cycle of therapy, and have had their disease re-evaluated will be considered evaluable for non-target disease. The response assessment is based on the presence, absence, or unequivocal progression of the lesions.

### 11.1.2 Disease Parameters

**Measurable disease.** Measurable lesions are defined as those that can be accurately measured in at least one dimension (longest diameter to be recorded) as  $\geq 20$  mm ( $\geq 2$  cm) by chest x-ray or as  $\geq 10$  mm ( $\geq 1$  cm) with CT scan, MRI, or calipers by clinical exam. All tumor measurements must be recorded in millimeters (or decimal fractions of centimeters). Tumor lesions that are situated in a previously irradiated area may only be considered measurable if they are growing on pre-treatment imaging.

**Malignant lymph nodes.** To be considered pathologically enlarged and measurable, a lymph node must be  $\geq 15$  mm ( $\geq 1.5$  cm) in short axis when assessed by CT scan (CT scan slice thickness recommended to be no greater than 5 mm [0.5 cm]). At baseline and in follow-up, only the short axis will be measured and followed.

**Non-measurable disease.** All other lesions (or sites of disease), including small lesions (longest diameter  $<10$  mm [ $<1$  cm] or pathological lymph nodes with  $\geq 10$  to  $<15$  mm [ $\geq 1$  to  $<1.5$  cm] short axis), are considered non-measurable disease. Bone lesions, leptomeningeal disease, ascites, pleural/pericardial effusions, lymphangitis cutis/pulmonitis, inflammatory breast disease, and abdominal masses (not followed by CT or MRI), are considered as non-measurable.

**Target lesions.** All measurable lesions up to a maximum of 2 lesions per organ and 5 lesions in total, representative of all involved organs, should be identified as **target lesions** and recorded and measured at baseline. Target lesions should be selected on the basis of their size (lesions with the longest diameter), be representative of all involved organs, but in addition should be those that lend themselves to reproducible repeated measurements. It may be the case that, on occasion, the largest lesion does not lend itself to reproducible measurement in which circumstance the next largest lesion which can be measured reproducibly should be selected. A sum of the diameters (longest for non-nodal lesions, short axis for nodal lesions) for all target lesions will be calculated and reported as the baseline sum diameters. If lymph nodes are to be included in the sum, then only the short axis is added into the sum. The baseline sum diameters will be used as reference to further characterize any objective tumor regression in the measurable dimension of the disease.

**Non-target lesions.** All other lesions (or sites of disease) including any measurable lesions over and above the 5 target lesions should be identified as **non-target lesions** and should also be recorded at baseline. Measurements of these lesions are not required, but the presence, absence, or in rare cases unequivocal progression of each should be noted throughout follow-up.

### 11.1.3 Methods for Evaluation of Measurable Disease

All measurements should be taken and recorded in metric notation using a ruler or calipers. All baseline evaluations should be performed as closely as possible to the beginning of treatment and never more than 4 weeks before the beginning of the treatment.

The same method of assessment and the same technique should be used to characterize each identified and reported lesion at baseline and during follow-up. Imaging-based evaluation is preferred to evaluation by clinical examination unless the lesion(s) being followed cannot be imaged but are assessable by clinical exam.

Clinical lesions. Clinical lesions will only be considered measurable when they are superficial (*e.g.*, skin nodules and palpable lymph nodes) and  $\geq 10$  mm ( $\geq 1$  cm) diameter as assessed using calipers (*e.g.*, skin nodules). In the case of skin lesions, documentation by color photography, including a ruler to estimate the size of the lesion, is recommended.

Conventional CT and MRI. This guideline has defined measurability of lesions on CT scan based on the assumption that CT slice thickness is 5 mm (0.5 cm) or less. If CT scans have slice thickness greater than 5 mm (0.5 cm), the minimum size for a measurable lesion should be twice the slice thickness. MRI is also acceptable in certain situations (*e.g.* for body scans).

Use of MRI remains a complex issue. MRI has excellent contrast, spatial, and temporal resolution; however, there are many image acquisition variables involved in MRI, which greatly impact image quality, lesion conspicuity, and measurement. Furthermore, the availability of MRI is variable globally. As with CT, if an MRI is performed, the technical specifications of the scanning sequences used should be optimized for the evaluation of the type and site of disease. Furthermore, as with CT, the modality used at follow-up should be the same as was used at baseline and the lesions should be measured/assessed on the same pulse sequence. It is beyond the scope of the RECIST guidelines to prescribe specific MRI pulse sequence parameters for all scanners, body parts, and diseases. Ideally, the same type of scanner should be used and the image acquisition protocol should be followed as closely as possible to prior scans. Body scans should be performed with breath-hold scanning techniques, if possible.

#### 11.1.4 Response Criteria

##### 11.1.4.1 Evaluation of Target Lesions

Complete Response (CR): Disappearance of all target lesions. Any pathological lymph nodes (whether target or non-target) must have reduction in short axis to  $< 10$  mm ( $< 1$  cm).

Partial Response (PR): At least a 30% decrease in the sum of the diameters of target lesions, taking as reference the baseline sum diameters.

Progressive Disease (PD): At least a 20% increase in the sum of the diameters of target lesions, taking as reference the smallest sum on study (this includes the baseline sum if that is the smallest on study). In addition to the relative increase of 20%, the sum must also demonstrate an absolute increase of at least 5 mm (0.5 cm). (Note: the appearance of one or more new lesions is also considered progressions).

Stable Disease (SD). Neither sufficient shrinkage to qualify for PR nor sufficient increase to qualify for PD, taking as reference the smallest sum diameters while on study.

#### 11.1.4.2 Evaluation of Non-Target Lesions

Complete Response (CR): Disappearance of all non-target lesions and normalization of tumor marker level. All lymph nodes must be non-pathological in size (<10 mm [<1 cm] short axis).

Note: If tumor markers are initially above the upper normal limit, they must normalize for a patient to be considered in complete clinical response.

Non-CR/Non-PD: Persistence of one or more non-target lesion(s) and/or maintenance of tumor marker level above the normal limits.

Progressive Disease (PD): Appearance of one or more new lesions and/or *unequivocal progression* of existing non-target lesions. *Unequivocal progression* should not normally trump target lesion status. It must be representative of overall disease status change, not a single lesion increase.

Although a clear progression of “non-target” lesions only is exceptional, the opinion of the treating physician should prevail in such circumstances, and the progression status should be confirmed at a later time by the review panel (or Principal Investigator).

#### 11.1.4.3 Evaluation of Best Overall Response

The best overall response is the best response recorded from the start of the treatment until disease progression/recurrence (taking as reference for progressive disease the smallest measurements recorded since the treatment started). The patient's best response assignment will depend on the achievement of both measurement and confirmation criteria.

**Table 5: For Patients with Measurable Disease (i.e., Target Disease)**

Target Lesions	Non-Target Lesions	New Lesions	Overall Response	Best Overall Response when Confirmation is Required*
CR	CR	No	CR	≥4 wks. Confirmation
CR	Non-CR/ Non-PD	No	PR	
CR	Not evaluated	No	PR	
PR	Non-CR/ Non-PD/ not evaluated	No	PR	≥4 wks. Confirmation
SD	Non-CR/	No	SD	Documented at least once

	Non-PD/ not evaluated			≥4 wks. from baseline
PD	Any	Yes or No	PD	no prior SD, PR or CR
Any	PD**	Yes or No	PD	
Any	Any	Yes	PD	

* See RECIST 1.1 manuscript for further details on what is evidence of a new lesion.
 
** In exceptional circumstances, unequivocal progression in non-target lesions may be accepted as disease progression.
 
Note: Patients with a global deterioration of health status requiring discontinuation of treatment without objective evidence of disease progression at that time should be reported as “symptomatic deterioration.” Every effort should be made to document the objective progression even after discontinuation of treatment.
				

**For Patients with Non-Measurable Disease  
(i.e., Non-Target Disease)**

Non-Target Lesions	New Lesions	Overall Response
CR	No	CR
Non-CR/non-PD	No	Non-CR/non-PD*
Not all evaluated	No	not evaluated
Unequivocal PD	Yes or No	PD
Any	Yes	PD

* ‘Non-CR/non-PD’ is preferred over ‘stable disease’ for non-target disease since SD is increasingly used as an endpoint for assessment of efficacy in some trials so to assign this category when no lesions can be measured is not advised
		

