disease progression after cytotoxic chemotherapy; results revealed median progression free survival (mPFS) of 9.7-16.7 months as stratified by prior octreotide therapy (8). RADIANT-2 was a Phase III trial that evaluated Everolimus in advanced, non-functional NETs of the lung or GI tract which revealed mPFS of 11 months as compared to 3.9 months in the placebo group (9). RADIANT-3 was a Phase III trial that evaluated Everolimus in advanced, low-grade or intermediate grade pancreatic NET that revealed an 11 month mPFS compared to 4.6 months with placebo (10). RADIANT-4 was a Phase III trial that evaluated Everolimus in advanced, non-functional NETs of the lung or GI NET that reported an 11 month mPFS compared to a 3.9 month mPFS with placebo (11).

Thoracic NETs are histopathologically subdivided into typical carcinoid (TC) and atypical carcinoid (AC) tumors(12) and comprise 2.2% of lung cancers diagnosed in the US annually (7, 13). AC is the more common and more aggressive phenotype. There is a paucity of data regarding systemic therapy for advanced thoracic NET disease outside of the recently published RADIANT-4, and is based mainly on small retrospective series and subgroup analyses of predominant gastrointestinal neuroendocrine tumor clinical trials, leading to a lack of definitive data for systemic regimen recommendations outside of everolimus placebo (11). Forde et al., reported on a systematic analysis of thoracic NET patients at Johns Hopkins. The response rate to platinum plus etoposide chemotherapy for both advanced TC and AC was 23.5% (14).

GI NETs arise in the stomach, intestine, appendix, colon or rectum with an incidence of approximately 8000 cases annually in the US(15). The 5-yr OS rates in advanced well and moderately-differentiated neuroendocrine tumors range from 14-54% by anatomic location. The PROMID study showed an improvement in time to tumor progression in advanced midgut NET patients treated with octreotide LAR (long acting release (2) The recent advances of use of Everolimus in the RADIANT series have shown improved outcomes in some endpoints, leading to FDA approval, but does not frequently cause a response with tumor shrinkage (9, 11).

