### **3. PATIENT SELECTION**

#### **3.1 Eligibility Criteria**

- 3.1.1 Subjects with histologically confirmed advanced, progressive, well-differentiated nonfunctional NET of the pancreas, lung or gastrointestinal (GI) tract per the 8th International Association for the Study of Lung Cancer classification (IASLC) or the American Joint Committee on Cancer (AJCC) Staging Handbook, 7th edition. Progression must be documented over the prior 12 months.
- 3.1.2 Measurable disease by CT or MRI per RECIST 1.1 criteria (Appendix 3); radiographic tumor assessment performed within 28 days before treatment. Target lesions may be located in a previously irradiated field if there is documented (radiographic) disease progression in that site after the completion of radiation therapy.
- 3.1.3 Prior therapy, including everolimus, octreotide, surgery, chemoradiation, is all permitted after being properly noted. This prior therapy must have been completed at least 28 days prior to study enrollment.
- 3.1.4 Patients with lung NETs must have progressed after at least 1 line of therapy. Patients with GI NETs must have had at least 2 lines of prior therapy.
- 3.1.5 Subjects are to have tumor tissue sample available at central lab for PD -L1 IHC testing during the screening period. Subjects can initiate therapy before the result of IHC testing.
- 3.1.6 (Stage 2 only) Subjects must be willing to undergo 2 sets of core needle biopsies (pre-treatment and at 6-8 weeks on therapy) if there are lesions amenable to biopsy. Subjects without a lesion amendable to biopsy will still be permitted to enroll provided they have an archival tumor sample for PD-L1 IHC testing. An optional core biopsy will be requested at progression.

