### 12.3.2 Secondary Endpoints

Secondary endpoints include safety and tolerability of study treatment; PFS, DCR, DOR and OS in the all treated subjects population.

Safety and tolerability objectives will be measured by the incidence of adverse events, serious events, deaths, and laboratory abnormalities. Dates and duration of study treatment delays will also be described.

PFS is defined as the time from first dose to the date of the first documented tumor progression (per RECIST 1.1), or death due to any cause. Clinical deterioration in the absence of radiographic evidence is not considered progression for purposes of determining PFS. Subjects who die without a reported prior progression will be considered to have progressed on the date of their death. Subjects who did not progress or die will be censored on the date of their last evaluable tumor assessment.

Subjects who did not have any on study tumor assessments and did not die will be censored on the first dosing date. Subjects who started any palliative local therapy or subsequent anti-cancer therapy without a prior reported progression will be censored at the last evaluable tumor assessment prior to initiation of the palliative local therapy or subsequent anti-cancer therapy, whichever procedure occurred first. PFS rate at 6 months is defined as the rate from Kaplan-Meier estimate 6 months after first dosing date.

Disease control rate is defined as the number of subjects with a BOR (per RECIST v1.1 criteria) of confirmed CR or PR or SD (stable disease), divided by the number of treated subjects.

Duration of response will be summarized among subjects with objective response in and is measured from the time at which the criteria for objective response are first met until the date of a progression event (according to the definition of PFS). Subjects with objective response who does not have a progression event will be censored at the same time they were censored under the definition of PFS.

Overall survival is defined as the time from first dosing date to the date of death. A subject who has not died will be censored at last known alive date. The overall

survival rate at 6 months is the rate from Kaplan-Meier estimate 6 months after dosing date.

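### The disease control rate counts any stable disease at the first scan, so on the protocol's own placebo medians it barely separates an active from an inactive regimen

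*Combined protocol and SAP*

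**What the plan says.** DCR is listed as an efficacy measure in objective 1.2.3. Section 12.3.2 defines it as a proportion, with numerator and denominator "of confirmed CR or PR or SD (stable disease), divided by the number of treated subjects". No minimum duration of SD is given there, and section 11.1.5, which defines the duration of SD, sets no threshold either.

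The only minimum is in Table 5 (section 11.1.4.3), where SD qualifies as best overall response if "Documented at least once", "≥4 wks. from baseline".

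On scan timing, section 11.1 says "For the purposes of this study, patients should be re-evaluated every 6 weeks", and note e of the Study Calendar (section 9) says later scans "may be done within +/- 7 days of intended visit". The baseline assessment is a "radiographic tumor assessment performed within 28 days before treatment" (3.1.2).

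For the course of disease without active treatment, section 2.1 describes a lung/GI everolimus trial that "reported an 11 month mPFS compared to a 3.9 month mPFS with placebo", and a pancreatic trial with 11 against 4.6 months.

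Section 12.4.2 describes a different DCR analysis: a Kaplan-Meier median among subjects with a confirmed complete or partial response.

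**The concern.** A minimum duration for SD is meant to keep out subjects who have simply not yet had time to progress. Here it cannot do that. The first scheduled scan already falls more than 4 weeks after baseline, so every subject whose first scan shows no progression is credited with disease control, whatever the next scan shows.

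The trial has a single arm, and the documents give no null value, threshold or comparator for DCR. Section 2.4.1 benchmarks the response rate against everolimus and placebo but does nothing similar for DCR. A DCR near 80% could therefore be presented as benefit when it fits the placebo curves the protocol itself cites.

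**Working it through.** **The plan's own figures.** The documents state no expected or null DCR. The only design calculation is the Simon two-stage design for response rate in 12.2. An exact binomial calculation with 20/1 and 56/4 at 5% and 15% gives early termination 0.736, expected size 29.51, and errors 0.097 and 0.199, all as stated. None of these depends on SD.

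**Step 1: does the 4-week minimum exclude anyone?** The first scan is due at week 6 with a window of 7 days either way, so at weeks 5 to 7 from first dose. If baseline is the first dose, the interval is 5 to 7 weeks. If it is a scan up to 28 days earlier, the interval is up to 11 weeks. Both exceed 4 weeks, so the rule never binds at a scheduled scan.

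**Step 2: DCR with no active drug.** Inputs are the placebo medians of 3.9 and 4.6 months and, for an active drug, the 11-month median, all from section 2.1. The assumption is that PFS is exponential and that the cited arms resemble this population. With *t* in months (4.348 weeks per month) and median *m*:

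S(t) = exp(−ln 2 × t/m)

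At week 6, t = 6/4.348 = 1.380 months. For m = 3.9, S = exp(−0.6931 × 1.380/3.9) = exp(−0.245) = 0.783. The other entries follow in the same way:

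| Scan | m = 3.9 | m = 4.6 | m = 11 | Gap (points) |
|---|---|---|---|---|
| Week 6 | 78.3% | 81.2% | 91.7% | 10-13 |
| Week 12 | 61.2% | 66.0% | 84.0% | 18-23 |
| Week 24 | 37.5% | 43.5% | 70.6% | 27-33 |

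Across the visit window (weeks 5 to 7) the no-drug figure is 75-84%.

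**Step 3: sensitivity to curve shape.** With a Weibull curve, S(t) = exp(−ln 2 × (t/m)^k), and k from 0.8 to 1.5:

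- Week 6: no drug 74-89%; 11-month median 88-97%; gap 8-14 points.
- Week 24: no drug 31-45%; 11-month median 67-78%; gap 22-47 points.

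**Step 4: against the trial's precision.** With 56 treated subjects, 0.783 × 56 = 44 and 0.812 × 56 = 45 would have disease control without an active drug. The exact 95% interval for 44/56 is 66-88%; for 51/56 (91%, near the 11-month figure) it is 80-97%. These overlap widely. At week 24, 21/56 (37.5%) gives 25-51% and 40/56 (71%) gives 58-83%, which do not overlap. With the 4.6-month median, 24/56 (43%) gives 30-57%, just short of 58%.

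**Step 5: would a 6-week minimum help?** No. The first scan would still normally satisfy it, and the figure stays at 78-81%. Only a minimum tied to a later scan changes the result.

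**The case against.** The strongest reply is that the plan already provides what is wanted. Objective 1.2.2 specifies PFS at 6, 12 and 24 months, and 12.3.2 and 12.4.2 give the Kaplan-Meier method. A DCR requiring no progression at week 24 would nearly repeat 6-month PFS. DCR carries no hypothesis or decision, and a reader can set it beside PFS in the same report. This stands as mitigation and limits the weight of the point. It does not make the DCR itself informative.

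A second reply is that "of confirmed CR or PR or SD (stable disease), divided by the number of treated subjects" might require SD to be confirmed as well. Table 5 points the other way, since it asks for SD only once. Were SD confirmed at week 12, the no-drug figure would fall to 61-66%, so the wording should be made explicit.

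A reader might also infer more than the documents support:

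- **That the 4-week number or the baseline anchor causes the high figure.** It does not. The figure comes from counting any SD at the first scan. Although 28 days may separate the baseline scan from first dose, section 11.1.4.3 counts best response from the start of treatment and no scan is scheduled before week 6. The anchor could matter only for an unscheduled early scan, such as the reassessment before palliative local therapy in 4.2.2.7.
- **That 78-81% is a prediction.** It is an illustration. This population is pretreated (3.1.4), the cited arms may differ from it, and subjects never scanned stay in the denominator and lower the rate. Section 2.1 also gives the same 11 against 3.9 months for two different trials, so the 3.9 needs some caution.
- **That the tumours are so slow-growing that the result is inevitable.** Placebo medians of 3.9 to 4.6 months do not show that. Week 6 is simply early relative to those medians.

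**Conclusion.** The point holds as a limited improvement to a secondary, descriptive endpoint. As defined in 12.3.2 with Table 5, DCR is essentially the proportion without progression at the first scan. Under exponential PFS at the cited medians, that is about 78-81% without an active drug (74-89% over the shapes tried) against 92% for an 11-month median. A gap of 10-13 points is hard to see with 56 subjects. At week 24 the same assumptions give 37-44% against 71%.

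The primary response-rate decision is untouched, and nothing here suggests that the trial's main conclusion is at risk. Separately, 12.4.2 contradicts 12.3.2: a Kaplan-Meier median among responders excludes SD and is not a rate.

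**What to change.** 1. Leave Table 5 as it is. A long SD minimum there would leave a subject who is stable for several scans and then progresses without a clear best-response category, because the PD row requires no prior SD.
2. In 12.3.2, add a duration-qualified DCR: confirmed complete or partial response, or SD with no progression at a scheduled scan well beyond the first, timed from first dose, over all treated subjects. Week 24 with the visit window is one workable choice. It is a scheduled scan, it sits close to the 6-month PFS objective, and 25 weeks (25/4.348 = 5.75 months) falls before the primary analysis six months after the last subject's first treatment. Other late scans are defensible.
3. Report it alongside the any-SD DCR, labelled as control at first scan, and state that confirmation applies to complete and partial response only.
4. In 12.4.2, replace the Kaplan-Meier median of DCR among responders with a binomial proportion and exact confidence interval in all treated subjects, so that it agrees with 12.3.2.

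The cost is a few sentences in two sections, with no new scans, visits or subjects. The headline DCR becomes less favourable, and the new measure overlaps with 6-month PFS.
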